We intend to recruit local (residing in the San Francisco Bay Area), outpatient adult veterans with chronic musculoskeletal pain to enroll in this clinical trial. This research proposal will use randomization after baseline assessments to assign participants (n=30) to at-home teleyoga or in-person yoga (n=15 per group). Randomization will occur by identifying group membership in 30 sealed envelopes and having each participant draw one envelope. To be representative of the veteran population at VAPAHCS Health Care System (VAPAHCS) each group will have 1-2 females.

All human subjects research will be performed at VAPAHCS in Palo Alto, California or at the homes of the veterans (residing in the San Francisco Bay Area) who receive the at-home teleyoga group. There are no other collaborating sites where human subjects research will be performed.

Month					
1	2	3	4	5	6
Recruit (n=30)			Run in-person yoga groups (n=15) Run at-home teleyoga groups (n=15)		

Table 1. Recruitment Table

Group assignment and randomization

Eligible participants will be added to a cohort list; when 30 have been identified, the study team will schedule baseline assessments. After the baseline assessments, participants will be randomized to in-person or at-home teleyoga (n=15 per group). Randomization will occur by identifying group membership in 30 sealed envelopes and having each participant draw one envelope. Each group will contain 1-2 females, to be representative of the veteran population at VAPAHCS.

Statistical Plan and Data Analysis

Fidelity and Missing Data Benchmarks

Fidelity: The instructors will review the video recorded sessions using a manual checklist for instructor adherence to the yoga manuals, which will consist of a Yes/No for each procedure or instruction.

Missing Data: Like similar behavioral outcome measures, we expect missing data in the PROMIS-PI measures not to exceed 15%.

The main analytic strategy will be descriptive statistics at pre- and post-intervention assessments in each arm. We will then preliminarily compare the two conditions in line with the intention to treat principle. The purpose of these comparisons is not to provide formal inference but provide preliminary information to guide the adequately powered future trial.

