The estimated changes and their group differences in pain and depression measured by the BPI-SF and BDI-II will provide preliminary data on target engagement and therefore inform and shape the future trial in terms of elucidating the mechanism of action. We will make a rigorous effort to minimize missing data. Nonetheless, we expect some attrition by post-intervention assessment. For group comparisons, we will focus on collecting preliminary data on clinical significance (i.e. effect size), instead of making formal inference (i.e., *p*-value).

Inclusion/Exclusion Criteria

Identify inclusion criteria.

- Veteran of the United States Armed Forces ≥ 18 years old
- Diagnosis of chronic musculoskeletal pain > 6 months (Dworkin, 2012)
- Minimum pain intensity at screening visit: pain rated ≥ 4 on a 0-10 Numeric Rating Scale (NRS) as recommended by IMMPACT guidelines. We intend to use the NRS from the Defense and Veterans Pain Rating Scale (DVPRS).
- Has not begun new pain treatments or medications in the past month.
- If on a psychotropic medication regimen: stable regimen for at least 4 weeks prior to entry to the study; willingness to remain on a stable regimen during the 12-week acute treatment phase.
- English literacy.
- Wireless internet connection at home.

Identify exclusion criteria.

- Participation in another concurrent clinical trial.
- Back surgery within the last 12 months.
- Back pain potentially attributed to a specific underlying cause, disease, or condition.
- Baseline pain < 4 or ≥ 9 on a 0-10 Numeric Rating Scale (NRS) as recommended by IMMPACT guidelines. We intend to use the NRS from the Defense and Veterans Pain Rating Scale (DVPRS). For ratings ≥ 9 , we will refer the veteran to the provider for prompt care.
- Unstable, serious coexisting medical illness.
- Unstable, serious coexisting mental illness or psychiatric conditions.
- practiced yoga ≥ 1 x in the past 12 months
- Active current suicidal intent or plan.

Criteria will be applied based on the informed consent process, a review of the participant's VA electronic medical record (EMR) and a screening interview.

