The informed consent process, including the HIPAA document, is estimated to take about 30-60 minutes. It will take place in a quiet office or interview room, or via video link.

1. The Project Manager will explain the information contained in the written informed consent (purpose, procedures, risks, benefits, alternatives to participation, etc.) and HIPAA documents to the study candidate verbally, in lay language.

- a. The Project Manager will check for comprehension, allow the study candidate ample opportunity to ask questions throughout the process, and repeat the information, as necessary.
 - b. Care will be taken to inform the study candidate that his/her participation is entirely voluntary, and they may withdraw at any time and for any reason without penalty or loss of benefits to which they would otherwise be entitled.
 - c. Study candidates will then be asked to carefully read the informed consent form to consider whether or not to participate in the research and to ask questions.
 - d. To ensure that the study candidate understands the research, they will next be asked to summarize the consent form and HIPAA addendum, with a special focus on the discomforts, risks, benefits, and confidentiality sections.
2. If the study candidate demonstrates (by stating in his/her own words) an understanding of the purpose, risks, and benefits of the study and agrees to participate in the study, he/she will be asked to initial each page, in addition to sign and date the last page of the consent form and the HIPAA document.
 3. The Project Manager who oriented and obtained informed consent will sign and date the informed consent form.
 4. The Project Manager will provide the enrolled participant with a photocopy of the original signed copy and keep the original signed copy in a binder in a locked cabinet.

The emphasis on the voluntary nature of participation is designed to minimize the possibility of coercion or undue influence on participation. The study candidate will be given time to understand the written informed consent form and make an informed decision. All treatments for this study will be provided in group formats, so potential participants will be reminded that full anonymity cannot be maintained.

Following the informed consent process, the enrolled participant will complete other measures.

Screening Procedures

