Potential participants (n=30) will be invited to the VAPAHCS for a screening visit. The Project Manager will obtain informed consent and review the Health Insurance Portability & Accountability Act (HIPAA) document. After obtaining informed consent, a trained researcher will collect demographic information (Demographic Questionnaire). Screening for protocol eligibility will include the Clinical Questionnaire and DVPRS.

Study Assessments

Demographics Questionnaire: Documents age, gender, education, and race/ethnicity.

Clinical Questionnaire: Self-report document focusing on the existence of 78 health symptoms taken from a list of ICD-9 codes that are highly likely to represent chronic pain.

Medication Use: Self-report of all current pharmacological and non-pharmacological treatments.

Yoga Home Practice Log: Log for participant to document their yoga home practice on non-treatment days.

BDI-II Beck Depression Inventory-II (BDI-II): Contains 21 self-report questions, scored on a 0-3 scale, related over the past two weeks to sleep, appetite, punishment, suicide, and interest in sex.

Brief Pain Inventory-Short Form (BPI-SF): Assesses intensity and impact of pain on functioning on a 0-10 rating scale. Interference is assessed on daily life (general, walking, work, mood, enjoyment, relationships, sleep). The BPI is recommended by the Initiative on Methods, Measurement, and Pain Assessment in Clinical Trials (IMMPACT) group for inclusion in clinical trials evaluating pain.

Defense and Veterans Pain Rating Scale (DVPRS): A five-item scale: one 0-10 pain intensity numeric rating scale and four supplemental items measuring functional outcomes (general activity, sleep, mood, level of stress). The pain intensity scale is designed to improve upon existing scales by using visual cues and word descriptors to anchor pain ratings with perceptual experiences and limitations imposed by pain.

PEG: A 3-item pain measure derived from the Brief Pain Inventory and validated in ambulatory care settings. It includes 1 severity item (average pain) and 2 interference items (enjoyment of life and general activity).

Patient-Reported Outcomes Measurement Information System-Pain Interference

(PROMIS-PI) (108): Examines the extent to which pain hinders engagement over the past seven days with social, cognitive, emotional, physical, recreational activities, and physical functioning through Likert-type 1-5 scales.

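### Optional improvement: estimate the exploratory BPI-SF and BDI-II arm differences by ANCOVA on the baseline score, and report them with a 95% confidence interval

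*Combined protocol and SAP*

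**What the plan says.** All references are to the Combined protocol and SAP. Under Statistical Plan and Data Analysis, the main strategy is descriptive: pre- and post-intervention statistics by arm. The arm comparison comes second: "We will then preliminarily compare the two conditions in line with the intention to treat principle". Its purpose is not formal inference but to "provide preliminary information to guide the adequately powered future trial".

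For the two clinical scales the same section says: "The estimated changes and their group differences in pain and depression measured by the BPI-SF and BDI-II will provide preliminary data on target engagement". These data will "therefore inform and shape the future trial in terms of elucidating the mechanism of action". On how group comparisons are reported: "we will focus on collecting preliminary data on clinical significance (i.e. effect size), instead of making formal inference". On missing data, "we expect some attrition by post-intervention assessment"; no rate is given.

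The section names no estimator beyond changes and their differences, no baseline covariate, and no interval or other measure of uncertainty. Study Assessments describes the BPI-SF as a scale that "Assesses intensity and impact of pain on functioning on a 0-10 rating scale". It therefore yields an intensity and an interference score, and the plan does not say which one is compared.

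Group assignment and randomization places the draw after the baseline assessments, with 15 per arm. Table 2 schedules BPI-SF and BDI-II at baseline and post-treatment.

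**The concern.** Once p-values are set aside, the estimate and its uncertainty are all that this comparison delivers, and the plan specifies neither in full. If the estimate is a plain difference in mean change, it takes the whole of any chance baseline gap off the post-treatment difference. The data usually support removing only a part, namely the regression slope of post-treatment on baseline. This adds avoidable noise, and 15 per arm is a size at which noise matters. An effect size without an interval also does not show the designers of the next trial how imprecise it is.

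The stake is modest. Neither scale appears in a hypothesis or among the listed feasibility outcomes. What could suffer is the guidance that the plan itself wants to pass to the next trial.

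**Working it through.** **The plan's own figure.** There is none to reproduce. N=30 (15 per group) is given without a power or precision calculation.

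**Inputs.** From the documents: n = 15 per arm; baseline measured before randomisation; both scales measured at both visits. Assumed, because the documents are silent: pre-post correlation r from 0.3 to 0.8; ratio k of post-treatment SD to baseline SD of 1.0 or 1.3; independent participants.

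**Formulas.** In units of the baseline SD, with slope rk, the variance of the arm difference is proportional to:

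- change score: 1 + k² − 2rk
- ANCOVA: k²(1 − r²) × (2n − 3)/(2n − 4). The last factor is the price of estimating the slope, 27/26 = 1.038 at n = 15.

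**Variance ratio, ANCOVA to change score, n = 15**

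| r | k = 1: change | k = 1: ANCOVA | ratio | k = 1.3: change | k = 1.3: ANCOVA | ratio |
|---|---|---|---|---|---|---|
| 0.3 | 1.40 | 0.945 | 0.675 | 1.91 | 1.597 | 0.836 |
| 0.5 | 1.00 | 0.779 | 0.779 | 1.39 | 1.316 | 0.947 |
| 0.7 | 0.60 | 0.530 | 0.883 | 0.87 | 0.895 | 1.029 |
| 0.8 | 0.40 | 0.374 | 0.935 | 0.61 | 0.632 | 1.036 |

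With equal SDs the cut is 32%, 22%, 12% and 6%. With k = 1.3 it is 16% and 5%, then a loss of 3% and 4%. Simulation of normal scores agrees: 0.677, 0.778, 0.879 and 0.932 for k = 1 (20,000 trials per setting); 0.837, 0.949, 1.028 and 1.038 for k = 1.3 (40,000 per setting).

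**Where the gain comes from.** Before the 27/26 factor, the two variances differ by (1 + k² − 2rk) − k²(1 − r²) = (1 − rk)². That is the variance that chance baseline imbalance adds to a change-score difference. At k = 1, r = 0.5: 1.00 − 0.75 = 0.25 = (1 − 0.5)². At k = 1.3, r = 0.7: 0.87 − 0.8619 = 0.0081 = (1 − 0.91)², which is too small to repay the slope. Removing imbalance and gaining precision are therefore one benefit, not two.

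**Narrowed baseline spread.** Entry requires a pain rating of at least 4 and below 9 (Inclusion/Exclusion Criteria), so equal SDs may flatter ANCOVA for pain. As an assumption, halve the baseline variance and keep the slope r and residual variance 1 − r² of the k = 1 case. The change-score variance becomes 0.5(1 − r)² + (1 − r²) = 1.155, 0.875 and 0.555 at r = 0.3, 0.5 and 0.7. ANCOVA stays at 0.945, 0.779 and 0.530. The cuts fall to about 18%, 11% and 5%.

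**95% half-width.** t × √(2/n × variance term), with t on 2n − 3 df for ANCOVA and 2n − 2 for change; k = 1, in SD units:

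| r | change, n = 15 | ANCOVA, n = 15 | ANCOVA, n = 12 (assumed attrition) |
|---|---|---|---|
| 0.3 | 0.885 | 0.728 | 0.830 |
| 0.5 | 0.748 | 0.661 | 0.753 |
| 0.7 | 0.579 | 0.545 | 0.621 |

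For r = 0.5 with ANCOVA at n = 15: √(2/15 × 0.779) = 0.322, times t = 2.052, gives 0.661. In units of the post-treatment SD, k² cancels, so for a given r the ANCOVA width does not depend on k.

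**The case against.** **This is exploratory, and ANCOVA is a preference.** Largely fair. The plan disclaims inference, and at r = 0.7 with equal SDs the half-width moves only from 0.579 to 0.545 SD. No planning decision is shown to turn on that. This is why the point is optional. The missing interval is the firmer part, since it does not depend on r, and an interval read as estimation fits the plan's stated approach.

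**The comparator is assumed.** A reader might infer that the plan commits to an unadjusted change-score analysis, or that its estimate would be biased. The documents support neither. The wording does not exclude adjustment, and under randomisation the change-score difference is unbiased. The precision figures are savings against the natural reading only.

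**The two arms both receive yoga.** This stands. The arm difference contrasts two delivery modes and says little about whether yoga engages its target. Within-arm change, which the plan also reports, bears on that more directly.

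**ANCOVA on participants with both scores drops those lost to follow-up.** This stands too. The plan invokes intention to treat and expects attrition without fixing an analysis set, so the fix must not present such a fit as a solution.

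**Clustering.** Because "All treatments for this study will be provided in group formats" (Informed Consent Process), a reader might infer that the interval would be seriously too narrow. With an assumed ICC of 0.05 and one class of 15 per arm, the design effect is 1 + 14 × 0.05 = 1.70 and simulated coverage about 87%. But the documents give neither ICC nor class size, and Table 1 speaks of groups in the plural in each arm. With classes of 5, the design effect is 1 + 4 × 0.05 = 1.20 and coverage about 93%. A caveat is warranted, not a headline.

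**PEG and PROMIS-PI are left out.** They are collected at the same two visits, but the plan's sentence on group differences names only BPI-SF and BDI-II.

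**Conclusion.** The point holds as a cheap, optional improvement to an exploratory analysis, not as an error in the plan. Over the assumed range, ANCOVA changes the variance of the arm difference by anything from a 32% cut to a 4% loss. Smaller gains are more plausible for pain if the entry window narrows the baseline spread. These figures rest on assumed r and SD ratio, a common slope and independent participants.

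The more dependable benefit is the interval. At 15 per arm the arm difference is known only to within roughly 0.5 to 0.7 SD either way for r between 0.3 and 0.7, even with the better estimator. Leaving the BPI-SF score unnamed is missing detail that the same edit settles; it is not a separate fault. A reader might infer that the feasibility conclusions or the sample size are in doubt. They are not: neither rests on this comparison.

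**What to change.** In Statistical Plan and Data Analysis, state the following.

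- For BPI-SF intensity, BPI-SF interference and BDI-II, each taken separately, the arm difference in the post-treatment score is estimated by ANCOVA with the baseline value of the same score as covariate. Participants are analysed in the arm to which they were randomised.
- The result is given in scale points with a 95% confidence interval and no p-value. Any standardised difference names its divisor, and its interval is called approximate.
- The number without a post-treatment score is reported by arm, with a statement that a fit to participants with both scores does not resolve attrition.
- The intervals treat participants as independent although classes are given in groups, so they may be too narrow.
- The arm difference contrasts two delivery modes of yoga. Within-arm change is reported alongside, as already planned.

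Cost: a paragraph of SAP text, a few lines of code and one degree of freedom. No new data are needed. The possible downside is a small loss of precision if the post-treatment SD is well above the baseline SD and r is about 0.7 to 0.8.

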Feasibility of at Home Telehealth Yoga for Treating Chronic Pain

Study Protocol and Statistical Analysis Plan

NCT #: 04074109

November 22, 2021

Background

Chronic pain is a debilitating condition with high societal and economic costs. Pharmacological pain management includes opioids, which can be dangerous and ineffective after long-term use. Consequently, increased efforts are being made to find nonpharmacological treatment options for the management of chronic pain. For this reason, rigorous research on complementary and integrative health (CIH) for pain is a top priority and pain is the condition for which adults in the United States most often use complementary and integrative health. Chronic pain, and especially musculoskeletal pain is even more prevalent among veterans, and yoga has emerged as a popular and effective treatment option. The use of yoga to treat chronic pain has been endorsed by many organizations including the NIH, the American College of Physicians, and the VA. However, patients, especially rural and low-income patients, can encounter many barriers to practicing yoga, including travel costs and time, health conditions, bad weather, lack of transportation, and family responsibilities. One solution to overcome these barriers is to provide yoga at home using internet-based technology ("teleyoga"). Indeed, the provision of VA care via telehealth to increase access to those living far from VA medical facilities is a VA priority. Teleyoga is an innovative, potentially effective approach for treating chronic pain in veterans. Research evaluating the acceptability or efficacy of teleyoga is very limited. Our pilot data indicate that teleyoga is safe and has similar efficacy to in-person yoga for treating several common conditions in veterans, including chronic musculoskeletal pain (Schulz Heik et al., 2017). However, our teleyoga experience is limited to group yoga instruction via an audiovisual link to one or more outpatient clinics. This clinic-based modality requires participants to travel to a clinic for yoga instruction and does not overcome the multiple barriers associated with in-person care. Attempts by other groups to deliver at-home teleyoga have not overcome all the technical barriers encountered (Donesky et al., 2017). Standard Video conferencing software offers an exciting opportunity to develop at-home teleyoga using a well-resourced, scalable, and technologically advanced system. This study will focus on the treatment of chronic musculoskeletal pain, as it is the most common type of chronic pain in veterans and nonveterans (Kerns, 2018) and responds well to yoga.

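### The between-arm effect size from 15 per arm is equated with clinical significance, without an interval or an external benchmark, and is too imprecise to bear that reading

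*Combined protocol and SAP*

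**What the plan says.** The primary aims are feasibility and satisfaction (Specific Aims and Hypothesis; Study Design). The Statistical Plan and Data Analysis puts within-arm description first: "The main analytic strategy will be descriptive statistics at pre- and post-intervention assessments in each arm". The arms are compared after that, with this aim: "The purpose of these comparisons is not to provide formal inference but provide preliminary information to guide the adequately powered future trial".

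On the clinical scales the same section says: "The estimated changes and their group differences in pain and depression measured by the BPI-SF and BDI-II will provide preliminary data on target engagement". It adds that this will help to shape the future trial by clarifying the mechanism. For the arm comparisons it then says "we will focus on collecting preliminary data on clinical significance (i.e. effect size), instead of making formal inference".

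Allocation is given under Group assignment and randomization: "participants will be randomized to in-person or at-home teleyoga (n=15 per group". The documents give no SD, expected difference, minimal important difference, margin or attrition rate. They plan no interval for the arm difference and do not state the future trial's hypothesis.

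**The concern.** An effect size measures magnitude, usually in SD units. Whether a difference of that size matters to patients is a separate question, and answering it needs an external benchmark such as a minimal important difference in scale points. The plan treats the two as the same thing and supplies no benchmark.

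Dropping the p-value does not solve this. What remains is a point estimate with no stated measure of its uncertainty. At this sample size a chance difference of 0.5 SD, in either direction, could be reported as clinically significant and carried forward as guidance for the next trial.

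**Working it through.** **Inputs.** 30 participants, 15 per arm (Group assignment and randomization). The only check possible on the plan's own figure is 30/2 = 15, because N = 30 is given without a power or precision calculation. No SD is given, so everything below is in units of the SD of the measure compared. Assumed: 95% two-sided intervals, independent participants, roughly normal outcomes, and 15 down to 12 completers per arm.

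**Precision of the arm difference.** SE = √(2/n); half-width = t(0.975, 2n − 2) × SE.

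| Completers per arm | SE (SD units) | 95% half-width (SD units) |
|---|---|---|
| 15 | √(2/15) = 0.365 | 0.75 |
| 13 | √(2/13) = 0.392 | 0.81 |
| 12 | √(2/12) = 0.408 | 0.85 |

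At 15 per arm, the noncentral-t 95% interval around an observed d of 0.5 runs from −0.23 to 1.22. Around an observed d of 0.3 it runs from −0.42 to 1.02.

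**Effect of the assumptions.** Baseline adjustment narrows the half-width at 15 per arm to 0.65 SD if the pre-post correlation is 0.5, and to 0.54 SD if it is 0.7 (both assumed). Shared classes would widen it. With classes of 15 and an assumed intraclass correlation of 0.01 to 0.05, the multiplier is √(1 + 14 × ICC) = 1.07 to 1.30.

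**Chance findings when the true difference is zero.** Observed d divided by 0.365 follows a t distribution with 28 df.
- |d| > 0.3: 0.3/0.365 = 0.82, two-sided probability 0.418.
- |d| > 0.5: 0.5/0.365 = 1.37, two-sided probability 0.182.

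**What would follow if the observed d were used for sizing** (the plan does not say so). For superiority at 80% power and two-sided 5%, n per arm = 2 × ((1.96 + 0.842)/d)².
- d = 0.3: 174.4, so 175 per arm.
- d = 0.5: 62.8, so 63 per arm.
- If the true d were 0.3, the central 90% of observed values runs from −0.31 (wrong direction) to 0.94. The latter gives 18 per arm instead of 175.

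**What the pilot can supply, roughly.** Limits for the pooled SD are √(28/χ²) with 28 df, or 0.79 to 1.35 times the estimate. Sample size goes with the SD squared, so this is a range of 0.63 to 1.83 times in n. For an assumed pre-post correlation of 0.5, the 95% interval is about 0.17 to 0.73 with all 30 participants.

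**The case against.** The strongest reply is that the plan is modest and already says so. It disclaims formal inference twice. Its main analysis is within-arm description, and its primary outcomes are feasibility measures. In context, the sentence may only contrast magnitude with a p-value, and the effect size is not defined as Cohen's d, so it could be a difference in points. Descriptive statistics by arm would ordinarily include SDs, and retention and instrument completion are already outcomes. All of this stands, and it limits the point.

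Three stronger readings are tempting, and the documents support none of them.
- A reader might infer that the effect size is the pilot's main product. It is the focus of the group comparisons only.
- A reader might infer that the observed difference will size the next trial or decide whether it goes ahead. The text says only that the comparisons will "provide preliminary information to guide the adequately powered future trial". The use named for the BPI-SF and BDI-II differences is target engagement and mechanism. No go/no-go rule uses the arm difference.
- A reader might infer that the expected difference is about zero and that the next trial must be non-inferiority. The Background says teleyoga "has similar efficacy to in-person yoga", but it then notes that this experience was clinic-based. The future trial's comparator and hypothesis are not given.

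The reply does not remove the equation of effect size with clinical significance, the missing interval and benchmark, or the stated role of the comparisons in guiding the next trial. Reporting in raw points would not help by itself, since the half-width is still 0.75 times the scale's SD.

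**Conclusion.** The point holds for the between-arm comparisons and no further. At 15 per arm the 95% half-width is about 0.75 SD, or 0.81 to 0.85 SD with an assumed 13 to 12 completers. With a true difference of zero, |d| exceeds 0.3 in about 42% of pilots and 0.5 in about 18%. Such an estimate cannot show clinical significance, and it would be unreliable for sizing a trial if it were used for that.

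The feasibility and satisfaction aims are unaffected. The figures assume independent participants and no baseline adjustment. Adjustment at the assumed correlations leaves the half-width above 0.5 SD, so the conclusion does not turn on it. Whether the next trial should be superiority or non-inferiority is left open. The change should be made because the present wording gives an incorrect reading of the comparison, and correcting it needs no new data.

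**What to change.** In the Statistical Plan and Data Analysis, delete the equation of clinical significance with effect size and replace that sentence with text such as:

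*Arm differences in BPI-SF and BDI-II will be reported in raw scale points with 95% confidence intervals, as descriptive results. The pooled within-arm SD and the pre-post correlation of each scale will be reported with 95% confidence intervals, alongside retention and instrument completion. The target difference or margin of any future trial will be set from sources outside this pilot. The observed arm difference will not by itself size or stop that trial.*

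The cost is SAP wording and a few extra summaries. Both scales are already scheduled at baseline and post-treatment (Table 2), so no participants or visits are added. The pilot loses a headline effect size. The SD and correlation are themselves only roughly estimated, so their intervals should be carried into any later sample-size calculation.
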